5.4.3.2 LYNX Intervention Arm

Study staff will assist participants in downloading the mobile app, provide instruction on its use, and

help set up reminders to input sex diary entries. Study staff will use an onboarding document to walk participants through the download procedures and use of the app. These reminders will be personalized by the user for day, time, and message content at the first visit, and can subsequently be updated by participants if desired. Participants will be encouraged to explore and use other components of the app, the Sex Pro score, PrEP videos, sexual history diary, chat feature, and geo-location features. Users receive quarterly HIV/STI testing reminders using the mobile device notification feature. For confidentiality purposes, reminder notifications are nonspecific, but inside the app the participant is linked to their customizable testing reminder. Reminders include two options for testing: (1) the ability to order a home HIV/STI testing kit to be mailed free of charge, or (2) a geo-located map of the closest HIV/STI testing sites. PrEP uptake components will be finalized in the formative phase of this study.

5.4.3.3 Control Arm

Participants randomized to the control condition will be instructed to access HIV/STI testing at existing sites in the community. They will be provided with a list of these testing sites, along with an informational brochure about PrEP. All participants will be provided access to Sex Pro (risk assessment tool that is part of LYNX and will be made available online) after completion of the study.

5.4.3.4 Study Follow-up

All enrolled participants will be followed for 24 weeks. After enrollment, all follow-up visits will occur online, with SMS reminders, email, and phone follow-up conducted as needed to ensure completion of study procedures. Participants will complete an online CASI at 12 and 24 weeks and receive a stipend for completion of procedures at each study visit. Visit windows will be approximately 14 days before/after the target date. Participants will also be able to obtain additional home HIV self-test kits during the study follow-up, if needed. At the 3 month visit, any persons who have a positive HIV test plus up to 20 participants randomized to the LYNX arm will participate in an in-depth interview conducted by UCSF/SFDPH study staff via video-conferencing. The purpose of this interview is to elicit feedback on their experiences using the app, any technical difficulties encountered, and how the app could be further improved. Participants will be selected for interviews using purposive sampling based on level of engagement with the app, whether participants completed HIV/STI testing and/or initiated PrEP during the study, and to achieve diversity based on sociodemographics (e.g. age, race/ethnicity). Additionally, we will offer interviews to all participants who have a confirmed HIV diagnosis. In addition to asking about their experiences using the app, these participants will also be asked about additional information or support that would have been helpful at the time of receiving a positive HIV test result, and their experiences in getting linked to HIV care. By purposively sampling certain participants for the exit interviews, the goal is to select "information-rich cases from which one can learn a great deal about issues of central importance to the purpose of the research."⁵¹ All interviews will be audio recorded for transcription and analysis. Participants will be reimbursed for completion of each study visit according to local study site guidelines.

We will also conduct medical record abstraction for participants in this study. The goal of the medical record abstraction is to explore whether it is feasible to collect more objective measures of HIV and STI

testing and PrEP uptake, and to compare the medical records to self-reported data on these measures. Medical record abstraction will occur following the completion of the final follow-up assessment and will cover the entire study period. This abstraction will only occur if the participant has signed a medical records release form for the institution where records are being requested from. Signing a medical record release is not a requirement of enrollment—participants may refuse without being withdrawn from the study. SRV staff will not review the medical records of participants who do not sign a medical record release form. For participants who do sign medical record release form(s), only records verifying HIV and STI testing information, and records related to PrEP initiation will be requested. The period of abstraction will begin at the baseline visit and end up to 12 weeks following the 6 month follow-up assessment in order to accurately capture any PrEP initiation activity following mobile app use. Standard study CRFs with study ID will be completed using the medical records, and all medical records will be immediately de-identified (black out any identifiers) and labeled with study ID.

5.5 Research Staff Training

All proposed study staff have participated in the required trainings in participation and conduct of studies that involve human subjects, and any future study staff will do so upon hiring. Training for all research staff includes (but is not limited to) an overview of the study, study procedures and human subjects issues (informed consent process, confidentiality), a demonstration of all technology components, methods for establishing comfort with the sensitive issues, including discussion of sexual behaviors, that will likely arise in the course of the focus groups or assessments, review of the study instruments, their required elements and the inherent flexibility built into them, Human Subjects Protection, Good Clinical Practice, informed consent, quality management, confidentiality, and reporting of adverse events. As appropriate, site research staff will conduct mock visits of study procedures prior to enrollment of study participants.

5.6 Intervention Monitoring/Quality Control

A study checklist will be used to ensure that the research staff member assists participants in downloading the app, provides instruction on its use, and explains the relevant app features and sets up customizable features (e.g., reminders for HIV testing).

App analytics, including logins to the app and use of different app components, will be monitored for the technical pilot and pilot RCT phases of this project. Any issues that are detected will be discussed with the protocol team and site research staff, and a remediation plan will be developed and implemented at the sites.

6.0 EVALUATIONS AND MEASURES

Below is a summary of the measures for each aim of the study.

6.1 Formative phase (focus groups and in-depth interviews) (Aim 1)

6.1.1 Pre-entry or screening evaluations/measures (online survey)

- *Basic sociodemographics*
- *Eligibility questionnaire*

6.1.2 Quantitative assessment (online/paper assessment)

- *Demographics*
- *HIV/STI testing history, PrEP use history*
- *Sexual Risk and Drug Use Behaviors*
- *Technology use*

6.1.3 Qualitative assessment (Focus group/in-depth interview guide)

- *Overall feedback on the interface, appeal and usability;*
- *Ways to maximize acceptability*
- *Components that they like and/or dislike, and areas for improvement*
- *Feedback on specific content and functionalities guided by IMB model*
- *Attitudes regarding documenting their testing practices and results through signed medical releases, or sending photos of test results via a secure, HIPAA-compliant website*

6.2 Technical pilot (Aim 2)**6.2.1 Pre-entry or screening evaluations/measures (Online survey)**

- *Basic sociodemographics*
- *Eligibility questionnaire*

6.2.2 Pre-intervention (baseline) evaluations/measures (CASI)

- *Level of PrEP interest*
- *Sexual and drug use behaviors*
- *IMB model constructs for HIV/STI testing and PrEP knowledge, attitudes, motivations, and behavioral skills*
- *Eco-social factors influencing uptake of prevention strategies*

6.2.3 On-Study evaluations/measures

- *Exit interview (qualitative interview)*
 - *Feedback on functionality, technical performance, errors and bugs*
 - *Overall experiences of using app*
 - *Feasibility and acceptability of methods to confirm HIV testing results*
 - *Feedback for further refinement*
- *Follow-up CASI (online survey)*
 - *Acceptability:*
 - *System Usability Scale: a validated 10-measure scale that assesses subjective usability of a system, or, in this case, an app. It is scored from 0 to 100, and a score of 50 or greater indicates that the app is acceptable.*
 - *Sexual and drug use behaviors*

- *App-Specific Measures (app analytics)*
 - *Frequency and duration of app use*
 - *Content and functionalities most and least utilized*
 - *Number of HIV/STI home testing kits, condoms and lube requested*

6.3 Pilot RCT (Aim 3)

6.3.1 Pre-entry or screening evaluations/measures (online survey)

- *Basic sociodemographics*
- *Eligibility questionnaire*

6.3.2 Pre-intervention (baseline) evaluations/measures

- *Full sociodemographics*
- *Level of PrEP interest*
- *Sexual and drug use behaviors*
- *HIV/STI testing history*
- *PrEP knowledge*
- *IMB model constructs for HIV/STI testing and PrEP knowledge, attitudes, motivations, and behavioral skills*
- *Eco-social factors influencing uptake of prevention strategies*

6.3.3 On-Study evaluations/measures

- *Acceptability*
 - *System Usability Scale: a validated 10-measure scale that assesses subjective usability of a system, or, in this case, an app. It is scored from 0 to 100, and a score of 50 or greater indicates that the app is acceptable**
 - *In-depth interview (qualitative)*
- *Feasibility: app analytics (frequency of logins, use of LYNX app components)*
 - *We will use app analytics to determine whether at least 60% of individuals randomized to the intervention condition opened the LYNX app at least one time after their initial introduction to the app by research staff**
- *App-Specific Measures*
 - *Frequency and duration of app use*
 - *Content and functionalities most and least utilized*
 - *Number of HIV/STI home testing kits, condoms and lube requested*
- *Preliminary efficacy*
 - *HIV and STI testing frequency*
 - *HIV/STI Testing: participants will be asked to self-report on frequency of HIV/STI testing since last assessment. The primary HIV/STI testing measure will be the proportion of participants who self-report at least one test during the follow up period. We will also explore the concordance of self-report with data collected by medical release and using data electronically self-reported in the app, including home testing kits provided by request through the app.*

- *PrEP interest and uptake*
 - *PrEP care linkage: participants will self-report whether, in the past 3 months, they made and attended a clinic appointment for PrEP initiation, whether they were prescribed PrEP, and whether they utilized PrEP. We will also explore the concordance of self-reported prep use with data on PrEP use collected by medical release.*
- *Sexual and drug use behaviors*
- *Access to and utilization of health care*
- *IMB model constructs for HIV/STI testing and PrEP knowledge, attitudes, motivations, and behavioral skills*
- *Eco-social factors influencing uptake of prevention strategies*
- *Potential moderators of the intervention (measured at baseline and follow-up visits)*
 - *Demographics: Age, student status, education level, income, living situation, employment, insurance status, depressive symptoms, anxiety, trauma, and abuse*

*Primary study endpoints

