Using the Information-Motivation-Behavior Skills (IMB) model, we have developed a highly interactive mobile app to promote accurate risk perception and increase HIV/STI testing and linkage to care among YMSM. Sex Pro (Sexual Health Promotion) is an innovative web-based tool that provides a personalized HIV risk score, based on data from several large MSM cohort studies.^{12,16,45,46} This score is displayed on a “speedometer” (1-20 scale), with a higher score representing a higher level of protection, and was highly predictive of HIV risk among Black MSM in HPTN 061, with all HIV infections occurring in individuals with a score below 16.⁴⁷ YMSM found it particularly useful and informative, but preferred a mobile app. Sex Pro has been developed into a mobile app, with additional features incorporated, including a sex diary to facilitate accurate data collection; HIV/STI testing information and reminders; and access to home HIV/STI testing options and geospatial-based testing site and linkage to HIV care information.

This study is part of the iTech NIH U19, which has the overall goal to develop innovative technology-focused interventions addressing the HIV prevention and care continuum for youth.

In this pilot project, we propose to develop a new app, LYNX, by leveraging our existing mobile app platform Sex Pro and incorporating key components for increasing PrEP uptake and refining this app to maximize acceptability among YMSM. We will then evaluate the acceptability and feasibility of this integrated app in a pilot randomized controlled trial (RCT) among YMSM at risk for HIV acquisition in the US. If found to be feasible and acceptable, LYNX will be tested for efficacy in increasing HIV testing and PrEP linkage in a separate efficacy RCT study as part of the iTech.

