3.0 STUDY DESIGN

Using an iterative process of app development, this study will be conducted in 3 phases: 1) formative research to refine LYNX with input from YMSM; 2) a technical open pilot to optimize functionality and technical performance; and 3) a pilot RCT to evaluate feasibility, acceptability, and preliminary efficacy of LYNX.

- **Formative Phase**

Guided by the IMB model, the LYNX app will be refined through an iterative design process informed by a series of focus groups and in-depth interviews in up to 40 YMSM to elicit feedback on content, usability, layout, and functionality of the LYNX app.

- **Technical Pilot**

The LYNX app will be tested in a 2 month technical pilot study in up to 15 YMSM to optimize app functionality and performance. Data will be used to further refine the app and finalize the intervention protocol, outcome measures, and assessment tools for the pilot RCT.

- **Pilot RCT**

60 HIV-uninfected YMSM will be enrolled into a 6 month pilot study evaluating the feasibility and acceptability of the LYNX app. Participants will be randomized 2:1 to receive the LYNX app or a standard of care control condition. Feasibility and acceptability will be assessed through app analytics of usage patterns (logins, use of app components) and acceptability scales administered via computer-assisted self interview. We will also evaluate preliminary efficacy by comparing the proportion of YMSM who test at least once during the 6 month pilot, and proportion who successfully link to a PrEP provider, in the intervention versus control groups.

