5.3 Randomization Procedures

Randomization will be used only for the pilot RCT. Only participants who express interest in using LYNX, meet eligibility criteria, provide informed consent, and complete a baseline assessment will be eligible for randomization. Subjects will be randomized 2:1 into either the LYNX intervention arm (N=40) or control arm (N=20).

The 2:1 allocation will allow us to efficiently gather additional data on app utilization. Randomization will be based on a pre-generated list created by the Analytic Core, with random blocks of size three or six, and stratified by site (Tampa, Chicago) and age (15-18, 19-24). After consent and baseline survey completion, the participant will be randomized (assigned to the next available random allocation). **LYNX Intervention Condition:** Individuals who receive LYNX will be given brief instructions on the purpose of the app, how to access it, and an overview of how to use it. Participants will be encouraged to explore all components of the app and use it routinely. **Standard of Care Condition:** Following screening, participants in both conditions will receive standard of care prevention material consisting of provision of information regarding recommendations for HIV testing and referrals to local HIV testing sites and prevention services.

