10.1.3 Pilot RCT (Aim 3)

Response rates to follow-up surveys will be tabulated by recruitment venue and respondent characteristics to help understand potential sources of bias. We will characterize the study population using descriptive statistics and compare the intervention and control groups at baseline using t-, Wilcoxon, and chi-square tests. Point estimates for mean SUS score ≥ 50 and for proportion accessing the app >0.60 will be considered the minimum criteria for acceptability and feasibility, consistent with industry standards.^{49,50} A secondary feasibility outcome will be achieved if $\geq 50\%$ of participants who open the app complete their personalized risk score at least once.

The secondary outcomes of preliminary efficacy of the LYNX app to increase HIV/STI testing (any testing over follow-up) and PrEP uptake (as described above) will be evaluated using unadjusted risk ratios for each outcome. If there is evidence of divergence from balance in measured baseline covariates (i.e., failure of randomization), post-hoc analyses using Poisson regression with robust standard errors will be used to estimate adjusted risk ratios. Outcome variables will represent any HIV testing and any PrEP uptake over the follow-up period. Separate models will be estimated for each outcome.⁵²

With 60 participants randomized 2:1 to intervention: control, and 10-20% attrition, we will have 80% power to detect 37-42 percentage point increases in HIV testing and PrEP uptake, depending on rates in controls. The lack of precision and large minimum detectable effects, typical of pilot studies, will entail careful interpretation of study results in the light of overall patterns, plausibility, and findings from other mHealth studies.

Qualitative data from exit interviews will be analyzed by the LYNX team using the methods described in Aim 1 and will inform efforts to finalize app revisions and prepare for efficacy evaluation of the app.

Note: Any deviations from the analysis plans outlined above or in the sections that follow will be documented and justified in the Statistical Analysis Plan developed for this protocol.

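### The primary feasibility cut-off is inclusive in section 6.3.3 (at least 60%) but strict in section 10.1.3 (>0.60), so 24 of 40 passes one rule and fails the other

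*Combined protocol and SAP*

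**What the plan says.** Section 6.3.3 (On-Study evaluations/measures) sets this feasibility test, to be judged from app analytics: "at least 60% of individuals randomized to the intervention condition opened the LYNX app at least one time after their initial introduction". The item carries the asterisk that the section explains as "Primary study endpoints". The other asterisked item is the System Usability Scale (SUS), for which "a score of 50 or greater indicates that the app is acceptable".

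Section 10.1.3 (Pilot RCT, Aim 3) sets the decision criteria as point estimates. It asks for a mean SUS score of at least 50, and states that a "proportion accessing the app >0.60 will be considered the minimum criteria for acceptability and feasibility". The next sentence adds a secondary feasibility criterion, also inclusive: at least 50% of those who open the app complete their risk score.

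Section 5.3 (Randomization Procedures) plans 40 participants in the LYNX arm and 20 in the control arm. Section 1.1 (Background) states the use of the result, which is a decision on a further trial: "If found to be feasible and acceptable, LYNX will be tested for efficacy in increasing HIV testing and PrEP linkage".

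**The concern.** The same endpoint has an inclusive threshold where it is defined and a strict one where it is analysed. The criterion is a bare point estimate, with no confidence bound and no intermediate zone, so at the boundary the sign alone decides the verdict. The planned arm of 40 makes the boundary attainable, because 60% of 40 is a whole number of people.

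If that count occurred, the team would have to choose between the two rules after seeing the data, on one of the two primary endpoints and on a finding that bears on whether LYNX moves to an efficacy trial.

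The strict sign also stands alone. SUS is inclusive in both sections and the secondary risk-score criterion is inclusive, which suggests a slip. The documents do not show which sign was meant.

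**Working it through.** **Inputs**
- Rule A (6.3.3): x/n >= 0.60.
- Rule B (10.1.3): x/n > 0.60.
- x = participants who open the app after the introduction; n = all randomised to LYNX.
- Planned n (3.0 and 5.3): 60 randomised 2:1, so 60 x 2/3 = 40. This reproduces the plan's own arm size.
- Expected opening rate p: not given in the documents. Values from 0.60 to 0.80 are assumed below.

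**Step 1. Minimum passing counts at n = 40.** 0.60 x 40 = 24 exactly. Rule A needs 24 or more (24/40 = 60.0%). Rule B needs 25 or more (25/40 = 62.5%). The rules disagree at x = 24 and nowhere else.

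**Step 2. Other arm sizes.** The rules can differ only if 0.60n is a whole number, that is, if n is a multiple of 5. From n = 34 to 46 that happens three times:

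| n | Minimum under A | Minimum under B |
|---|---|---|
| 35 | 21 | 22 |
| 40 | 24 | 25 |
| 45 | 27 | 28 |

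**Step 3. Chance of landing on the conflict count, given n = 40.** P(X = 24) = C(40,24) p^24 (1-p)^16. This equals the gap between the two chances of passing.

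| Assumed p | P(pass A) | P(pass B) | P(X = 24) |
|---|---|---|---|
| 0.60 | 56.8% | 44.0% | 12.8% |
| 0.65 | 79.8% | 69.5% | 10.3% |
| 0.70 | 93.7% | 88.5% | 5.2% |
| 0.75 | 98.8% | 97.4% | 1.5% |
| 0.80 | 99.9% | 99.7% | 0.2% |

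At p = 0.60 the corresponding chance is 13.7% for n = 35 (x = 21) and 12.1% for n = 45 (x = 27).

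**Step 4. How different the two minimum results are.** Exact (Clopper-Pearson) 95% intervals are 43.3% to 75.1% for 24/40 and 45.8% to 77.3% for 25/40. As evidence about the true opening rate they are almost the same.

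**Step 5. Allowing the arm size to vary.** Section 5.3 uses random blocks of three or six within four strata (two sites by two age groups), so incomplete final blocks can move the LYNX arm off 40. In a simulation of 60 participants (assumptions: block sizes equally likely; strata either equal or weighted 10/40/15/35%), the arm was exactly 40 in about 42% of runs. Nearly all other runs gave 38, 39, 41 or 42, where the rules agree. The unconditional chance of a conflict is then about 0.42 x 12.8% = 5.4% at p = 0.60, and about 4.3%, 2.2%, 0.6% and 0.08% at 0.65, 0.70, 0.75 and 0.80.

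**The case against.** The strongest reply is that this is editorial. It has four parts.

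1. *The probabilities assume an arm of exactly 40.* This is correct, and Step 5 shows the effect: once the arm size varies, each figure falls by more than half. Replacement of discontinued participants (6.3.4) could move the denominator further. The figures in Step 3 must therefore be read as conditional on n = 40. The contradiction at the planned size remains.

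2. *No numeric go/no-go rule is tied to this proportion.* Section 1.1 speaks only of being found feasible and acceptable, and SUS, app analytics and interviews also inform that judgement. This limits the consequence. But 10.1.3 does call the threshold a minimum criterion, so the verdict on the primary endpoint itself depends on the sign.

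3. *The strict sign may be an inclusive sign that lost its bar when the PDF was read.* This cannot be excluded and should be checked in the source PDF. It is not the likelier reading, because the inclusive signs before and after it in the same paragraph survived.

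4. *The wording about accessing the app is only shorthand for the 6.3.3 definition.* Agreed; it is not counted as a second contradiction. A cross-reference is still useful, because 5.1 and 5.4.3.1 treat LYNX participants as enrolled only after onboarding, whereas 6.3.3 counts everyone randomised and only openings after the introduction.

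**Conclusion.** The inconsistency holds as a minor point. As printed, the plan gives two thresholds for one primary endpoint, and at the planned arm of 40 a count of 24 meets one and fails the other. The effect is confined to a single count and disappears if the final arm size is not a multiple of 5. Under the assumed opening rates, the chance that it matters runs from 12.8% down to 0.2% given n = 40, and from about 5.4% down to 0.08% when the arm size follows the simulated blocks. A result at that count would be borderline under either sign. No estimate, sample size or procedure is affected. The conclusion takes the strict sign in 10.1.3 as printed, subject to a check of the source PDF.

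**What to change.** Use one inequality in both sections, fixed before the app-use data are seen. An inclusive >=0.60 (24 or more of 40) would match 6.3.3 and the form of the other two criteria in 10.1.3. A strict rule would also serve, provided 6.3.3 is changed to agree.

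In the same edit, have 10.1.3 refer to the 6.3.3 definition: opened at least once after the staff introduction, with everyone randomised to LYNX as the denominator. The criterion then cannot be read as counting the onboarding session or as leaving out people who were never onboarded.

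The cost is one sign and one cross-reference, with no change to data collection, sample size or conduct.
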